The results can be summarized as follows: No adverse effects were observed from the subcutaneous application of dendritic cells, except for one patient who showed mild fever and arthralgia. Immunological effects were observed in vitro in 60% of the treated patients through an increase in specific T lymphocyte precursors against tumor cells in the patient's blood measured by ELISPOT, in addition to delayed-type hypersensitivity reactions (DTH) in 50% of the treated patients when tumor extract was injected subcutaneously after vaccinations. Finally, partial regression or mixed response was observed in two patients. One showed regression of lung metastases, and the other showed regression of cutaneous metastases. In most cases, disease stability was observed, although it cannot be concluded that a significant relationship exists between vaccination and the survival of treated patients. These results motivate further exploration of the methodology, primarily intending to provide therapeutic alternatives to patients with no other options.

Theoretical Formulation of the Project

Melanoma is a malignant tumor of neuroectodermal origin whose incidence has progressively increased in the last century. The only way to cure a malignant melanoma is early detection and appropriate surgical treatment, as once it reaches an advanced state, it is highly resistant to conventional treatments such as surgery, radiotherapy, and chemotherapy (1-3). Globally, melanoma is the fastest-growing and most deadly type of skin cancer in Europe and the United States among various cutaneous cancer types. This situation is also observed in Chile; only in Santiago, between 1992 and 1996, 318 malignant melanoma cases were detected, representing 10.6% of all types of skin cancer (1). While it is true that malignant melanoma is almost entirely curable (>95%) when detected early, the survival probability in patients with metastatic melanoma decreases significantly (<15%). Although surgery, chemotherapy, and radiotherapy are the primary conventional methods for treating this disease, implementing new therapies is essential, especially in patients with stage III and IV melanoma, where chemotherapy and radiotherapy are ineffective.

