Cancer remains one of the leading causes of death, especially among residents of highly developed countries. Modern surgical techniques and transplants, new and more effective drugs, and improved irradiation methods have allowed promising results in treating some diseases. A clear example of this progress is reflected in the treatment of childhood leukemia with a new generation of anti-cancer drugs (2). Often, some malignant cells survive these therapies and spread throughout the body, necessitating the development of new treatments as alternatives or complements to current ones. One such approach is manipulating the immune system to combat tumors, known as cancer immunotherapy. Since the 1980s, when cytotoxic T lymphocytes (CTL) with antitumor activity were isolated from peripheral blood, lymph nodes, and tumor tissue of melanoma patients, there has been growing interest in using the immune system in cancer treatment. Cytokines such as Interleukin-2 (IL-2) and Interferon gamma (IFN- γ) are commonly used as alternative therapies (4,5) in some neoplasms, and adoptive therapies, using in vitro stimulated CTL, have been tested in some clinical protocols with varying responses (6).

Over the last thirty years, significant progress has been made in understanding the functioning of the immune system, especially regarding antigen recognition (3,7). On the other hand, the significant advances in molecular biology techniques that facilitate gene cloning and the production of recombinant proteins have allowed for identifying tumor-associated antigens (AAT) and their subsequent characterization.

Cytotoxic T Lymphocytes and Antitumor Immune Response

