- b) Immediately after treatment, the patient must be monitored. Vital signs should be taken 15 minutes before and after each treatment, and the patient should be observed in the clinic for at least one hour. After the observation period, the patient will be sent home.
- c) Interleukin-2 will be administered subcutaneously, on an outpatient basis, in a properly equipped outpatient clinic for three consecutive days. Vital signs will be monitored, and the patient will be observed in the clinic for 30 minutes.
- d) Patients will be followed to detect and evaluate potential toxic reactions to treatment. The next dose can be repeated the following week if: - There was no grade IV toxicity with the previous treatment, - There was no obvious disease progression - The patient does not meet the exclusion criteria for the protocol.

Inclusion Criteria:

- Patients with histologically confirmed melanoma of the skin: Breslow, Clark, histological type. Location of the primary, clinical, or pathological regional status.
- Complete staging demonstrating the presence of distant metastases, either visceral or in soft tissues or bone tissue: Brain, Lung, Abdomen, and Pelvis CT and bone scintigraphy.
- Objectively measurable disease by clinical or radiological means
- Karnofsky's Performance Status is more significant than 70%
- Life expectancy greater than three months
- Patients over 18 years old
- Informed consent from the patient to participate in the protocol

Exclusion Criteria:

Patients meeting any of the following criteria will be removed from the study:

- Age greater than or equal to 65 years
- Ongoing active infections, including viral immunodeficiency
- Previous chemotherapy within less than two months
- Concomitant malignant tumors (e.g., Chronic Lymphocytic Leukemia, etc.)
- Uncontrolled concomitant diseases (Hypertension, unstable Diabetes mellitus, renal diseases requiring dialysis)
- Situations or conditions requiring urgent surgical intervention, such as intestinal obstruction due to metastasis
- Pregnancy or lactation
- Concurrent participation in other therapeutic research protocols
- Any condition that compromises the objectives of this study.

Removal Criteria from the Study:

Patients will be removed from this study if any of the following conditions occur:

- By the patient's decision to discontinue the study.
- Intolerable adverse reactions, according to WHO Criteria Grading Toxicities

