- Intercurrent illness that may compromise the patient's life or interfere with the treatment study evaluation
- Requirements for concomitant medication that may interfere with study results.
- Failure to complete the study entirely
- Failure to follow up on the patient.

Sample Size

Recruitment will be conducted to terminate the study after a specific number of patients have been enrolled if a minimum number of responses have not been observed. The lowest significant response rate will be 20% ($\alpha = 0.10$; $\beta = 0.10$). If at least the minimum number of objective responses are observed to complete recruitment, 30 evaluable patients will be enrolled. For example, if there is no response in any of the first 12 treated patients or only 1 out of the first twenty, the study should be terminated. The confidence interval for the response rate is $>20\%$.

Evaluable Patient: An evaluable patient meets the inclusion criteria, does not meet any of the removal criteria, receives all four vaccination cycles, and has been clinically and radiologically followed until the end of this trial.

Study Conduct

- Signing of informed consent
- Complete medical history
- Complete physical examination
- Karnofsky Performance Status measurement
- Estimation of survival quality using the EORTC scale
- If applicable, photographs of the tumor and metastases
- Hematological studies, including albumin and total proteins.
- Electrocardiogram
- CD3, CD4, CD8 cell counts, and total lymphocyte count
- Blood sample collection for in vitro immunological studies.
- Staging radiological studies: Computed tomography of the brain, lungs, abdomen, and pelvis, and bone scintigraphy
- Estimation of metastasis size through physical and radiological examination
- Delayed hypersensitivity test (DTH)

Enrollment

After the procedures mentioned above, each eligible patient will be enrolled. Each patient will be given an identification number. Data will be maintained in a computerized file with restricted access for the research team for each patient.

Patient Monitoring

Patients will be clinically monitored once a week through the following parameters:

- Weight
 - Karnofsky Index
 - Vital signs
 - EORTC Quality of Life Index
 - Comprehensive physical examination
 - Monitoring for toxicity symptoms according to WHO Criteria Grading Toxicities and reporting adverse effects

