- Additionally, they will be evaluated through ELISPOT and ELISA assays, with blood samples taken before each vaccination, to assess the response of specific CTLs to DC stimulation and the presence of cytokines in the patient's serum.

Measurement at the End of Treatment

- Clinical evaluation of the patient
- Estimation of clinical or radiological tumor response: determining tumor volume
- Comprehensive physical examination
- Karnofsky Index
- Photography
- Quality of life and pain assessments
- Delayed hypersensitivity test (DTH): for in vivo response measurement
- Hematological and chemical tests: Assays for measuring in vitro immune response.

Long-Term Follow-Up

Once the patient has completed the full four-cycle treatment, they must be followed up every four weeks for one year. Every two months during the second year. The date of death must be determined in applicable cases. During each visit:

- Directed physical examination
 - Karnofsky Index
 - Estimation of clinical and radiological tumor size
 - Photography
 - EORTC Quality of Life Assessment
 - Reporting of adverse effects
- Clinical Response Assessment

TUMOR RESPONSE CRITERIA

CR: Complete disappearance of the tumor

PR: Tumor regression > 50%

MR: Tumor regression > 25% - <50%

SD: Decrease or growth < 25%

PD: Increase in tumor size during treatment

Statistical Analysis

The primary objective of this study is to estimate the objective response and toxicity associated with treatment using dendritic cells loaded when administered to patients with disseminated melanoma. A stratified recruitment design will be used in this study. In the first stage, 12 patients will be enrolled and treated with loaded dendritic cells. If none of the patients responds to the treatment, enrollment for this study will be terminated. If at least one patient responds to the treatment, the treatment will continue. If, after the enrollment of patient number 20, at least two patients respond to the treatment, the study should continue until a minimum of 30 evaluable patients with 3 out of 4 completed cycles. Assuming that the study will be completed with thirty patients as planned, the 90% confidence interval for the estimated response rate will be 12%, assuming a 20% response rate. If sufficient evidence indicates that the valid response rate is greater than 20%, it would be given if the lower limit of the confidence interval is more significant than 0.20 (alpha = 0.05, 1-tailed -test).

Primary Efficacy Analysis

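### Only prior chemotherapy has a washout, and no rule keeps a previously irradiated lesion out of CR/PR, so in this one-arm trial a carried-over regression would count as a response

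*Protocol*

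**What the plan says.** **Eligibility.** The only timed restriction on earlier treatment is the exclusion of "Previous chemotherapy within less than two months" (protocol, Exclusion Criteria). Three other clauses come near the subject:

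- "Concurrent participation in other therapeutic research protocols" (Exclusion Criteria) covers overlapping trials. It does not cover a completed trial or routine care.
- "Any condition that compromises the objectives of this study" (Exclusion Criteria) is left to judgement and names no treatment or interval.
- "Requirements for concomitant medication that may interfere with study results" (Removal Criteria from the Study) applies to medication needed on study, not to earlier therapy.

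**Response.** Patients need "Objectively measurable disease by clinical or radiological means" (Inclusion Criteria). The Tumor Response Criteria define CR as disappearance of tumour and PR as regression of more than 50%. They do not separate irradiated from non-irradiated lesions.

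**Decisions.** The Sample Size and Statistical Analysis sections stop the trial at 0 responses in 12 or only 1 in 20. After the first look the rule is: "If at least one patient responds to the treatment, the treatment will continue". The Primary Efficacy Analysis section says that the study is uncontrolled.

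**Background.** The Theoretical Formulation of the Project says that "surgery, chemotherapy, and radiotherapy are the primary conventional methods for treating this disease", and that IL-2 and interferon gamma "are commonly used as alternative therapies" in some neoplasms. The same group reports a completed phase I dendritic-cell vaccine trial in advanced melanoma.

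**The concern.** A washout exists because recent treatment can affect what is measured after entry. The protocol accepts this for chemotherapy but gives no reason for leaving out the other treatments its background names. A patient whose only measurable metastasis was irradiated shortly before entry, or who stopped IL-2 the week before, meets every listed criterion unless the investigator invokes the general clause.

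In a one-arm trial any regression after entry is credited to the study treatment. Delayed shrinkage of an irradiated lesion by more than 50% would be a PR. Two things are at stake: the continue/stop decision, which rests on one or two responses, and the reported response rate, whose estimation is a primary objective.

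**Working it through.** **Inputs from the protocol:** looks at 12 and 20 patients; continue with at least 1 and at least 2 responses; 30 evaluable patients; response rate of interest 20%; 90% confidence interval given as 12%; final criterion that the lower limit exceeds 0.20.

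**Inputs assumed:** the proportion *q* of entrants with a carried-over regression. The documents give no figure, so 2% and 5% are used as a range.

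**1. The plan's own figures.**

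- 90% half-width at 20% with 30 patients: 1.645 × √(0.2 × 0.8 / 30) = 0.120. This matches the stated 12%, read as plus or minus 12 points.
- At a true rate of 20%, P(0 of 12) = 0.8^12 = 0.069. P(stop at either look) = 0.8^12 + 12 × 0.2 × 0.8^19 = 0.069 + 0.035 = 0.103, in line with the stated β of 0.10.

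**2. Early looks with carry-over only.** Suppose the vaccine has no effect.

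- P(pass first look) = 1 − (1 − q)^12
- P(pass both) = 1 − [(1 − q)^12 + 12q(1 − q)^19]

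| q (assumed) | Pass first look | Pass both looks |
|---|---|---|
| 2% | 1 − 0.785 = 0.22 | 1 − (0.785 + 0.163) = 0.05 |
| 5% | 1 − 0.540 = 0.46 | 1 − (0.540 + 0.226) = 0.23 |

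With no vaccine effect and no carry-over or other regression, both figures are zero.

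**3. Early looks with a weak vaccine effect.** Assume a true rate of 5%, that 10–30% of patients had recent unrestricted treatment, and that 10–30% of those show a carried-over regression. The apparent rate is 0.05 + 0.95 × f × c:

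- lowest case: 0.05 + 0.95 × 0.1 × 0.1 = 0.0595
- highest case: 0.05 + 0.95 × 0.3 × 0.3 = 0.1355

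The probability of passing both looks rises from 0.23 without carry-over to 0.30 and 0.72.

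**4. Reported rate.** One carried-over response in 30 adds 1/30 = 3.3 points. At *q* of 2% to 5% the expected number is 30 × 0.02 = 0.6 to 30 × 0.05 = 1.5 patients. That is 2 to 5 points if the vaccine does nothing, ignoring the early looks.

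**5. Final criterion.** The exact lower 90% limit is 0.193 at 10/30 and 0.221 at 11/30, so at least 11 responses are needed. The probability of reaching 11/30 is below 0.002 in every scenario in step 3.

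**The case against.** The strongest reply has four parts.

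*The background does not suggest large carry-over.* The sentence naming radiotherapy as a conventional treatment goes on to call chemotherapy and radiotherapy ineffective in stage III and IV disease, and the account of the earlier vaccine trial calls them palliative. The remark on cytokines concerns some neoplasms, not these patients specifically. This stands: it makes a frequent carried-over PR less likely. It does not supply a rule for the one that occurs, and one is enough at the first look.

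*The early looks are futility rules, set low on purpose.* Passing them claims no efficacy. This also stands. A reader might infer that carry-over could make an inactive vaccine look successful; step 5 shows that the final criterion is hardly moved.

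*The immune aims are protected by baselines.* A reader might infer that recent IL-2 or an earlier vaccine would inflate the ELISPOT, cytokine and DTH results. The documents do not support a direction. Pre-treatment blood and a DTH test are taken (Study Conduct), with further blood samples before each vaccination (Patient Monitoring). A raised baseline would therefore be visible, and in a within-patient comparison it could mask a rise as easily as mimic one.

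*The investigator can already act.* A full medical history is taken and the general exclusion clause could be used. Accordingly, these treatments are not specifically excluded, rather than expressly permitted. But no rule tells the investigator when to use the clause, and none carries the history into the response assessment.

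**Conclusion.** The point holds in a limited form. The eligibility lists restrict prior chemotherapy by time and no other earlier treatment, and the response criteria would count regression of an irradiated lesion as CR or PR. The exposure is the continue/stop decision (23% chance of passing both looks at an assumed 5% carry-over with no vaccine effect, 5% at 2%) and 3.3 points on the reported rate per affected patient, against a half-width of about 12 points. The conclusion that the rate exceeds 20% is not materially at risk.

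The carry-over rates are assumptions. The documents give neither the frequency of recent prior treatment nor that of delayed regression, so the bias is possible, not shown. A reader might also infer that the two-month interval should simply be applied to every modality. Nothing in the documents supports that figure for other treatments, and its choice is a clinical matter.

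**What to change.** 1. In the Tumor Response Criteria, state that a previously irradiated lesion does not count toward CR or PR unless it has grown since irradiation.
2. Record the last prior therapy and its date for every patient at entry, and list both for each patient reported as CR or PR.
3. Add a sensitivity response rate that takes out of the numerator responders with recent non-chemotherapy treatment or earlier dendritic-cell vaccination. The sponsor should define recent for this purpose before any response is assessed.
4. Have the sponsor reconcile the chemotherapy-only washout with the other prior treatments named in its background, either by giving the reason for the difference or by stating a rule for each. Any interval is the sponsor's to choose.

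The cost is an amendment to the response section, one added data item and a short listing. A few patients may lack an assessable lesion, and the reported response rate may be slightly lower.

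### The two definitions of an evaluable patient conflict, and long-term visits are scheduled only for patients who complete all four cycles, so early stoppers, probably mostly non-responders, drop out of view

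*Protocol*

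**What the plan says.** **Who is evaluable.** The Evaluable Patient definition (Protocol, Sample Size) reads: "An evaluable patient meets the inclusion criteria, does not meet any of the removal criteria, receives all four vaccination cycles". It also requires clinical and radiological follow-up to the end of the trial. The removal criteria include failure to complete the study and intolerable adverse reactions. The Statistical Analysis section gives a different threshold: "the study should continue until a minimum of 30 evaluable patients with 3 out of 4 completed cycles".

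**When dosing stops.** Treatment, item d, allows the next dose only if there was no grade IV toxicity, if "There was no obvious disease progression", and if no exclusion criterion is met.

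**Who is followed.** Long-Term Follow-Up states: "Once the patient has completed the full four-cycle treatment, they must be followed up every four weeks for one year", then every two months in the second year. These visits cover tumour size, Karnofsky index, quality of life and adverse effects. The same paragraph adds: "The date of death must be determined in applicable cases". Measurement at the End of Treatment includes a tumour response estimate and is not expressly limited to completers.

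**Which patients are counted.** The interim rule stops the study "if there is no response in any of the first 12 treated patients", with a second look at twenty patients. The final target is "30 evaluable patients will be enrolled". Precision is given as: "Assuming that the study will be completed with thirty patients as planned, the 90% confidence interval for the estimated response rate will be 12" percent, at an assumed 20% response rate. The clinical response aim speaks only of a percentage of patients and names no analysis set.

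**The concern.** A patient who completes three cycles and then stops is evaluable under Statistical Analysis and not evaluable under Sample Size. This matters because the count of 30 decides when recruitment ends.

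The loss is also unlikely to be random. Doses are withheld for progression and severe toxicity, so early stoppers will tend to be patients doing badly. An early-stopped non-responder can count among the first 12 or 20 and then be absent from the final 30.

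The follow-up gap is harder to repair than the definition. An analysis plan can choose a denominator later, but it cannot recover visits that were never scheduled. Overall survival is a secondary aim, and toxicity is part of the primary objective. For both, patients who stopped early are among the most informative.

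**Working it through.** **Step 1. The plan's own figure.** Inputs from Statistical Analysis: response rate 0.20, n = 30, 90% interval. Half-width = 1.645 × √(0.20 × 0.80 / 30) = 0.120. This reproduces the stated 12%, so the precision was worked out for thirty patients, which is the evaluable target. That suggests, but does not establish, that the final rate is taken over evaluable patients.

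**Step 2. The passages side by side, by cycles received.**

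| Cycles received | Evaluable, Sample Size | Evaluable, Statistical Analysis | Scheduled long-term visits |
|---|---|---|---|
| 4 | yes, if the other conditions are met | yes | yes |
| 3 | no | yes | no |
| 1 or 2 | no | no | no |

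Weekly Patient Monitoring lists a physical examination but no imaging and no explicit tumour measurement, so it does not replace the missing visits.

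**Step 3. Effect on the estimate.** The Protocol gives no drop-out rate, so the number of uncounted treated non-responders is assumed. Start from 6/30 = 20.0%:

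- 2 more: 6/32 = 18.8%
- 4 more: 6/34 = 17.6%
- 8 more: 6/38 = 15.8%

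**Step 4. Effect on the criterion that the lower limit exceed 0.20 (illustrative).** The lower limit of the 90% interval is p − 1.645 × √(p(1 − p)/n) (Wald), or the exact Clopper-Pearson limit.

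| Responses/patients | Wald | Exact | Above 0.20? |
|---|---|---|---|
| 10/30 | 0.192 | 0.193 | no |
| 11/30 | 0.222 | 0.221 | yes |
| 11/32 | 0.206 | 0.206 | yes |
| 11/33 | 0.198 | 0.1995 | no |
| 11/34 | 0.192 | 0.193 | no |
| 12/34 | 0.218 | 0.218 | yes |
| 13/38 | 0.216 | 0.216 | yes |

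The smallest qualifying count is 11 of 30. At that count, three uncounted non-responders are enough to lose the criterion. One response more (12) survives four of them, and two more (13) survive eight.

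**Step 5. Chance of meeting the criterion at a true all-treated rate of 20% (illustrative).** Let a share s of treated patients be non-evaluable, with response rate q. The evaluable rate is then (0.20 − s × q)/(1 − s). Exact binomial probability of at least 11 of 30, ignoring the interim stops:

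| s (assumed) | q (assumed) | Evaluable rate | P(at least 11/30) |
|---|---|---|---|
| 0 | – | 0.200 | 2.6% |
| 10% | 0 | 0.222 | 5.2% |
| 20% | 0 | 0.250 | 10.6% |
| 30% | 0 | 0.286 | 21.5% |
| 20% | 10% | (0.20 − 0.02)/0.80 = 0.225 | 5.6% |

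The rows with q = 0 are the worst case. Letting one early stopper in ten respond roughly halves the 20% row.

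**The case against.** **The denominator is inferred.** No sentence restricts the final response rate to evaluable patients, and a half-width computed at n = 30 is a planning figure. An analysis plan may settle the set. This stands, so the bias in the response rate is conditional. The conflicting definitions and the completer-only visit schedule do not depend on it.

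**No formal tests are planned.** Primary Efficacy Analysis says so, because the study is small and uncontrolled, although Statistical Analysis gives a lower-limit criterion with a one-sided alpha of 0.05. This also stands. A reader might infer from Steps 4 and 5 that a planned test has an inflated error rate. The Protocol does not support that reading, because those figures show only how the criterion would behave if it were applied.

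**Early stopping may be rare or temporary.** Item d says when the next dose may be given the following week; it does not say that treatment ends for good. Progression is not itself listed as a removal criterion. Treatment lasts 60 days, and entry requires a life expectancy above three months and a Karnofsky score above 70%. These points limit how large the excluded group may be. They do not alter its likely make-up.

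**Some data on early stoppers may still be collected.** A reader might infer that they have no tumour or survival follow-up at all. That goes too far: the end-of-treatment measurement may cover them, and so may the date-of-death sentence. But the latter sits inside the completers' paragraph, and neither provides long-term visits. It would also go too far to call overall survival biased as planned, because the Protocol does not say which patients enter that analysis.

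**Conclusion.** The concern holds in limited form. The three-versus-four-cycle conflict is an error as written. Patients who stop before the fourth cycle have no scheduled long-term visits, and whether their deaths are recorded is unclear. Those patients are likely to be mostly non-responders, given the dosing rule.

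If the 30 evaluable patients form the denominator, the response rate tends to be too high. With 2 to 8 further treated non-responders, 20.0% falls to between 18.8% and 15.8%. The direction rests on early stoppers responding less often than completers; the size rests on a drop-out count that the Protocol does not give. The effect on the 0.20 criterion is confined to results near the 11/30 threshold and is worst-case where no early stopper is assumed to respond. The point is worth correcting because the remedy is cheap and missed follow-up is hard to rebuild afterwards.

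**What to change.** 1. **Long-Term Follow-Up:** start the schedule, including date of death, from the last dose received for every treated patient, unless consent to follow-up is withdrawn.
2. **Treatment item d and Removal Criteria:** state that a dosing stop or removal condition, other than withdrawal of consent to follow-up, ends study treatment only.
3. **Statistical Analysis:** report the response rate over all treated patients, with those who have no documented response counted as non-responders, at least beside the evaluable rate.
4. **Evaluable Patient and Statistical Analysis:** use one cycle threshold in both places.

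The cost is a few reworded sentences and one extra reported rate, with no added patients. The burden is continued contact with sicker patients; vital status can be obtained by telephone where visits are not feasible. The reported response rate may be somewhat lower.

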 - In vitro response: ELISPOT assays, measuring IFN- γ production in the peripheral blood of treated patients. Compare specific immune responses after each therapy cycle by measuring IFN- γ production by tumor-specific CTLs. Radioactive chromium releases cytotoxic assays to measure CTL and NK-mediated antitumor response. After each therapy cycle, ELISA assays for quantifying cytokines (IFN- γ , IL-10) in patient serum.
- **CLINICAL RESPONSE MEASUREMENT:** To observe the objective response rate. The percentage of patients with complete response (CR) and patients with partial response (PR) will be reported.

SECONDARY SPECIFIC AIMS:

To evaluate:

- Overall Survival.
- Disease-Free Survival.
- Quality of Life (assessed using EORTC global QLQ-C30 and EORTC disease-specific QLQ).
- Performance status response: The percentage of patients with a 20% or more significant increase in activity measured by the Karnofsky index will be reported.

MATERIAL AND METHODS

Dendritic Cell Generation: Patient leukocytes will be obtained through leukapheresis at the Blood Bank of the Clinical Hospital of the UNIVERSITY OF CHILE, following the standard protocols used in that unit. Peripheral blood mononuclear cells (PBMCs) will be isolated from peripheral blood using a Ficoll-Hypaque gradient. PBMCs will be cultured for 2 hours at 37°C and 5% CO₂ in a suitable serum-free clinical research medium, AIM-V Clinical Research® (Life Technologies, USA). Non-adherent cells will be discarded, and adherent cells (monocytes) will be cultured in AIM-V supplemented with 500 U/ml of recombinant IL-4 (R&D Systems, INC., MN, USA) and 800 U/ml of GM-CSF (R&D Systems, INC., MN, USA). On the sixth day, monocytes differentiated into dendritic cells will be pulsed with melanoma extracts and then matured with TNF- α (R&D Systems, INC., MN, USA). Flow cytometry will confirm mature dendritic cells' CD14⁻, CD36^{low}, and CD83^{high} phenotype characteristics. Mature DCs will be washed twice and resuspended in 300 μ l of sterile saline. All cell manipulation procedures for vaccine production will be performed under GMP conditions, as indicated.

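### The final response rate appears to rest on 30 evaluable patients, a set defined by events after treatment starts and by two conflicting cycle counts, so early failures drop out and the rate is likely biased upward

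*Protocol*

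**What the plan says.** - **Endpoint (Clinical Response Measurement).** "The percentage of patients with complete response (CR) and patients with partial response (PR) will be reported". No denominator is named.
- **Evaluable patient (Sample Size).** Besides meeting the inclusion criteria, the patient "does not meet any of the removal criteria, receives all four vaccination cycles, and has been clinically and radiologically followed until the end" of the trial. The target is 30 such patients.
- **Removal Criteria from the Study.** Among the reasons for removal is "Failure to complete the study entirely". Others are intolerable adverse reactions, intercurrent illness and loss to follow-up.
- **Treatment, item d).** One condition for the next dose is "There was no obvious disease progression".
- **Statistical Analysis, recruitment.** If the second look is passed, "the study should continue until a minimum of 30 evaluable patients with 3 out of 4 completed cycles". This is three cycles, where Sample Size has four.
- **Statistical Analysis, precision and decision.** "Assuming that the study will be completed with thirty patients as planned, the 90% confidence interval" is put at 12% for a 20% response rate. The rate is taken to exceed 20% "if the lower limit of the confidence interval is more significant than 0.20", with one-tailed alpha 0.05.
- **Early looks (Sample Size).** The study stops "if there is no response in any of the first 12 treated patients or only 1 out of the first twenty". These looks count treated patients.
- **Primary Efficacy Analysis.** No formal hypothesis tests are planned.

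**The concern.** Apart from the inclusion criteria, every condition for being evaluable is known only after treatment has begun. A patient who progresses, dies or withdraws before the required cycles fails the definition. Because recruitment runs until 30 evaluable patients exist, another patient takes that place. Nothing in the protocol counts the lost patient as a non-responder.

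Objective response is the primary efficacy result, and the stated aim is to estimate it in patients with disseminated melanoma. A rate among those who got through treatment answers a different question. It is too high whenever responders complete more often than non-responders. That is to be expected here, because early progressors are non-responders and are the patients denied further doses.

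Two further problems follow. The two cycle counts give different analysis sets: under three of four, a patient who progresses after the third cycle could stay in, while earlier failures still drop out. The denominator also changes from treated patients at the looks to evaluable patients at the end.

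**Working it through.** **The plan's own figure.** The 90% half-width at a 20% rate with n = 30 is 1.645 × √(0.20 × 0.80 / 30) = 0.120. This matches the stated 12%, so the precision statement does rest on 30 patients.

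**What the final rule requires at n = 30.** Exact one-sided 95% lower limits are 0.193 for 10/30 (not met) and 0.221 for 11/30 (met). Wald limits, 0.192 and 0.222, give the same cut-off. The rule therefore needs at least 11 responses.

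**Inputs**
- From the protocol: a 20% rate, 30 evaluable patients, stopping at 0 of 12 or at most 1 of 20 treated patients, and a lower limit above 0.20.
- Assumed, because the documents give no figure: *f*, the share of all treated patients who are not evaluable (10%, 20% or 40%), and *l*, the share of responders who are not evaluable (0, 10% or 20%).

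**Formula.** Response rate among evaluable patients = 0.20 × (1 − *l*) / (1 − *f*). For example, *f* = 0.20 and *l* = 0 gives 0.20 / 0.80 = 25.0%; *f* = 0.20 and *l* = 0.10 gives 0.18 / 0.80 = 22.5%.

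**Chance of meeting the rule.** This is the exact probability of passing both looks on treated patients and then having 11 or more responders among 30 evaluable patients, when the true all-treated rate is 20%. With no non-completion it is 2.6%.

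| Responders lost (*l*) | *f* = 10%: rate; chance | *f* = 20%: rate; chance | *f* = 40%: rate; chance |
|---|---|---|---|
| 0 (upper bound) | 22.2%; 5.2% | 25.0%; 10.5% | 33.3%; 40.2% |
| 10% | 20.0%; 2.6% | 22.5%; 5.6% | 30.0%; 26.3% |
| 20% | 17.8%; 1.1% | 20.0%; 2.6% | 26.7%; 14.8% |

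The bias is zero when *l* = *f* and downward when *l* > *f*.

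**A case where the conclusion flips.** At about 20% non-completion, 30 evaluable patients need 30 / 0.80 = 37.5, so 38, treated. Suppose there are 11 responders, all evaluable.
- 11/30 = 36.7%, exact lower limit 0.221: rule met.
- 11/38 = 28.9%, exact lower limit 0.172: rule not met.

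**The case against.** The denominator is inferred. No sentence says that the final rate is computed on evaluable patients only, the interval refers simply to thirty patients, and nothing speaks of replacement. A statistical analysis plan that is not at hand might name the analysis set. This stands as a limit on certainty. But the protocol itself defines the evaluable patient, makes that set the recruitment target, and does so with two different cycle counts. Followed as written, it has the effect described.

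Progression is not a listed removal criterion, and Tumor Response Criteria provides a category for tumour growth during treatment, so progressors may have been meant to be assessed. That is fair, but it does not override the cycle requirement.

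The direction is not certain. Evaluability also requires follow-up to the end of the trial, and Long-Term Follow-Up runs into a second year, so responders can be lost too. The table shows this: at 20% non-completion with 20% of responders lost, the bias is gone.

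The largest figures need heavy non-completion with no responder lost. Eligibility requires a life expectancy above three months and treatment lasts 60 days, which makes heavy loss during treatment less obvious. Against the stated alpha of 0.05, rather than the 2.6% that the rule actually delivers, the chances of 5.2% (10% non-completion, no responder lost) and 5.6% (20% non-completion, 10% of responders lost) are close to nominal. With no formal tests planned, the main harm is to the estimate. All of this stands and bounds the size of the problem; it does not remove it.

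**Conclusion.** The concern holds and should be fixed. The contradiction between four cycles and three of four is literal. That the final rate rests on evaluable patients is a strong inference from the recruitment target and the thirty-patient interval.

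For a true all-treated rate of 20%, non-completion of 10% to 20% with at most 10% of responders lost inflates the estimate by 0 to 5 percentage points. At 40% non-completion with no responder lost, the upper bound is 13.3 points (33.3% − 20.0%). The rule based on the lower limit is affected in the same direction. These sizes rest on assumed non-completion and responder-loss rates, and the upward direction rests on responders being lost less often than patients overall.

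**What to change.** - Define the primary response denominator as all eligible patients who received at least one vaccination. Count anyone without a documented CR or PR as a non-responder.
- Use this one set at the 12-, 20- and 30-patient points. The two looks already count treated or enrolled patients, so in practice mainly the final set changes.
- Judge eligibility on pre-treatment data only, so that this word does not bring in a new selection.
- Reconcile the two cycle counts, then keep the evaluable set as a labelled sensitivity analysis. Report how many treated patients it excludes and why.

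**Cost.** This is a change of wording, with no extra patients if the 30 become treated patients. The reported rate will probably be somewhat lower. The sensitivity analysis would hold about 27, 24 or 18 patients at 10%, 20% or 40% non-completion (30 × (1 − *f*)). Keeping 30 evaluable patients as well would need about 34, 38 or 50 treated (30 / (1 − *f*), rounded up).
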